#### 3-Month Follow-Up Visit (3 months ± 30 days since initial programming or consent date)

The following information will be collected at the 3-month follow-up visit:

- PDQ-39;
- UPDRS part II ADLs On Medication / On Stimulation;
- UPDRS part III motor examination Off Medication/Off and On Stimulation assessed by a blinded evaluator;
- UPDRS part III motor examination On Medication/ Off and On Stimulation assessed by a blinded evaluator;
- Omnidirectional testing – Off Medication (See Evaluation of Programming)
- Detailed directional lead testing as tolerated by the subject – Off Medication (see Evaluation of Programming); sites are to program each lead to the optimal directional segment;
- Programming parameters; device session data;
- Unscheduled visits (if applicable);

## Clinical Investigational Plan

- AE, system revision, and/or protocol deviation (if applicable).

### 6-Month Follow-Up Visit (6 months ± 30 days since initial programming or consent date)

The following information will be collected at the 6-month follow-up visit:

- PDQ-39;
- UPDRS part II ADLs On Medication / On Stimulation;
- UPDRS part III motor examination On Medication/ Off and On Stimulation assessed by a blinded evaluator;
- Programming parameters; device session data;
- Subject and clinician preference;
- Unscheduled visits (if applicable);
- AE, system revision, and/or protocol deviation (if applicable).

### 12-Month Follow-Up Visit (12 months ± 60 days since initial programming or consent date)

The following information will be collected at the 12-month follow-up visit:

- PDQ-39;
- Patient SUS questionnaire
- UPDRS part II ADLs On Medication / On Stimulation;
- UPDRS part III motor examination Off Medication/Off and On Stimulation;
- UPDRS part III motor examination On Medication/ Off and On Stimulation;
- Omnidirectional and directional testing - Off Medication;
- Programming parameters; device session data;
- Programmer SUS questionnaire;
- Unscheduled visits (if applicable);
- Current Parkinson's Disease medication;
- AE, system revision, and/or protocol deviation (if applicable).

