### Clinical Investigational Plan

	Subject is unable to comply with the follow-up schedule.
Data Collection	
Data will be collected at baseline, initial programming, and 3 months, 6 months, 12 months, 24 months and 36 months after initial programming date.
 
Retrospective chart review or prospective completion of the baseline study evaluations may be conducted for each subject. Retrospective collection of the most recently documented UPDRS part II ADLs and UPDRS part III motor scores (on and off medication) can be used as baseline data for comparison to 3-, 6-, 12- and 36-month data.
 
Subjects will undergo DBS system implantation in accordance with the physicians' standard operating procedures. Subjects will return for the initial programming visit according to the site's normal standard of care. The initial programming date will be classified as "Day 0". At the initial programming visit, the leads will be tested according to the site's standard monopolar review followed by omnidirectional testing. After Day 0, subjects will return to the clinic for evaluations at 3 months (<math>\pm 30</math> days), 6 months (<math>\pm 30</math> days), 12 months (<math>\pm 60</math> days), 24 months (<math>\pm 90</math> days) and 36 months (<math>\pm 90</math> days). At the 3- and 6-month visits, Parkinson's disease symptoms will be evaluated by a blinded evaluator using the UPDRS part III motor examination. At the 3-, 6- 12- and 36-month visits, subjects will be evaluated using the UPDRS part II for the ability to perform activities of daily living in the Stimulation On state, and will complete the PDQ-39 to evaluate quality-of-life. At the 3-, 12- and 36-month visits, a detailed omnidirectional and directional programming assessment will be performed. The right and left lead will be tested independently in multiple programming configurations. Amplitude will be increased slowly by the programmer until first meaningful therapeutic effect is confirmed by the blinded evaluator. Amplitude will continue to be increased slowly by the programmer until the first sustainable side effect is observed by the blinded evaluator.
 
The subject and programmer will also complete the System Usability Scale (SUS) at the 12-month visit to assess the ease of use of the device.
 
The PMCF requirement will be met when 66 subjects have been followed for 12 months and have evaluable primary endpoint at the 3-month follow-up visit.

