### 4.4.3 Descriptive Endpoints

The following data will be collected:

Evaluation of subject and clinician stimulation preference at 6-month follow-up visit;

Change in therapeutic effectiveness measured by UPDRS part III motor examination at the 12-month follow-up visit from baseline visit;

Change in ADLs as determined from the UPDRS part II ADLs at the 3-, 6-, and 12-month follow-up visits from baseline visit;

Change in quality-of-life as measured by the PDQ-39 at the 3-, 6-, and 12-month follow-up visits from baseline visit;

Evaluation of device-related adverse events;

Evaluation of subject and programmer satisfaction with product usability at the 12-month follow-up visit.

Comparison of mean values of therapeutic window with directional and omnidirectional stimulation;

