### 6.6 SCHEDULED FOLLOW-UPS

#### Blinded Evaluation

A blinded evaluator will be used in this study to minimize study bias. The blinded evaluator will assess the therapeutic window for each subject at the initial programming, the 3-month visit and at the 12-month visit. The UPDRS part III motor examination for each subject will also be assessed by the blinded evaluator at the 3-month and 6-month visits. This evaluator will not be aware of the subject's programming or device settings. It is recommended that the blinded evaluator assessing the therapeutic window and the UPDRS part III motor examination should be the same person; however, it is not required. In addition, subjects will be unaware of their programmed parameters for the first 6 months.

Subjects are to be instructed not to take medication the night prior to or the morning of the study visit. This is defined as the Off Medication state. Upon taking appropriate medication, subject is considered to be in the On Medication state.

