### 36-Month Follow-Up Visit (36 months ± 90 days since initial programming)

The following information will be collected at the 36-month follow-up visit:

- PDQ-39;
- UPDRS part II ADLs On Medication / On Stimulation;
- UPDRS part III motor examination Off Medication/Off and On Stimulation;
- UPDRS part III motor examination On Medication/ Off and On Stimulation.
- Omnidirectional and directional testing - Off Medication;
- Programming parameters; device session data;

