## Clinical Investigational Plan

The width of the therapeutic window is defined as the electrical current at which a sustained side effect appeared minus the electrical current at which a meaningful therapeutic benefit was obtained.

At the conclusion of the 3-month visit, the site physician should select the directional program that provides the best clinical benefit for the subject based on the detailed device testing that was completed and the subject should remain programmed using a directional configuration until the 6-month visit. If in the investigator's opinion, the directional configuration does not provide adequate therapy for the subject, the investigator may change the programming to allow the use of an omnidirectional configuration. Subjects who are implanted with the 4 channel lead will only have the omnidirectional testing at the initial programming visit to determine therapeutic window and first side effect. At the 3-month visit these subjects will complete the omnidirectional testing, will have the programming parameters collected and will complete the visit evaluations.

**12-Month Visit - Device testing is to be completed with the subject in the Off Medication state.** Omnidirectional and directional testing will be repeated according to the instructions above.

**36-Month Visit - Device testing is to be completed with the subject in the Off Medication state.** Omnidirectional and directional testing will be repeated according to the instructions above.

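### Month-12 UPDRS III has no blinded-rater requirement, although a blinded evaluator is already required at that visit for the therapeutic-window test

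*Combined protocol and SAP*

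**What the plan says.** The general rule is in Section 4.2 and in the Blinded Evaluation paragraph of Section 6.6, and the synopsis (Data Collection) agrees: UPDRS III is rated blind at months 3 and 6. The visit lists in Section 6.6 follow it. Month 3 has "UPDRS part III motor examination Off Medication/Off and On Stimulation assessed by a blinded evaluator" plus the On-Medication counterpart, and month 6 has "UPDRS part III motor examination On Medication/ Off and On Stimulation assessed by a blinded evaluator". The month-12 list gives "UPDRS part III motor examination Off Medication/Off and On Stimulation" and its On-Medication counterpart with no rater named. Month 36 is worded the same way: "UPDRS part III motor examination On Medication/ Off and On Stimulation".

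The therapeutic window follows a different rule. Section 6.6 says "The blinded evaluator will assess the therapeutic window for each subject at the initial programming, the 3-month visit and at the 12-month visit", so a blinded evaluator is part of the month-12 visit.

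The month-12 score is used in Section 4.4.3, where the descriptive endpoints include "Change in therapeutic effectiveness measured by UPDRS part III motor examination at the 12-month follow-up visit from baseline visit".

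On month-36 device testing, the synopsis says "At the 3-, 12- and 36-month visits, a detailed omnidirectional and directional programming assessment will be performed" and goes on to describe steps judged by the blinded evaluator. The 36-Month Visit paragraph under Evaluation of Programming says "Omnidirectional and directional testing will be repeated according to the instructions above". Table 1 and the two general blinding paragraphs do not show month 36 as blinded.

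**The concern.** UPDRS III is scored by a rater, and at month 12 it is scored with stimulation both off and on at the same visit. A rater who knows which state is which can lean towards the expected result, and nothing in the plan prevents that at month 12. The safeguard is already partly in place: the plan puts a blinded evaluator in that visit for the window test but does not give that person the motor score.

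What is at stake is the credibility of the month-12 motor result, which the plan labels a measure of therapeutic effectiveness. It would also be rated by a different method from the month-3 and month-6 scores reported beside it.

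**Working it through.** No arithmetic applies. The question is who rates what at which visit, so the sources are set side by side. In Table 1 an asterisk means blinded evaluation.

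| Visit | UPDRS III in the Section 6.6 visit list | UPDRS III in Table 1 | Device testing in Table 1 | Window test blinded in Sections 4.2 and 6.6 |
|---|---|---|---|---|
| Initial programming | not collected | none | X* (initial testing row) | yes |
| Month 3 | four states, blinded evaluator named | X* in four rows | X* | yes |
| Month 6 | two On-Medication states, blinded evaluator named | X* in two rows | X (no window test at this visit) | not applicable |
| Month 12 | four states, no rater named | X in four rows | X* | yes |
| Month 36 | four states, no rater named | X in four rows | X | not listed |

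**Step 1: is the month-12 gap real?** Yes. The general paragraphs, the visit list and Table 1 all agree, so it is not a damaged table or a single dropped phrase. The rater is left unspecified; the plan does not call for an unblinded one.

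**Step 2: is a blinded evaluator already required at month 12?** Yes, by Sections 4.2 and 6.6 and by the asterisk on device testing in Table 1.

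**Step 3: is the extra work feasible?** Month 3 is the comparison. There the blinded evaluator covers omnidirectional and directional testing and four UPDRS III states (medication off or on, by stimulation off or on). Month 12 has the same testing and the same four states. The plan already asks for this combined load once, so no new role or procedure is needed.

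**Step 4: which analyses use the month-12 score?** Section 12.1 has three hypothesis tests. The primary and the first secondary use the month-3 window. The second secondary compares UPDRS III at month 3 with month 6. All rest on blinded ratings, and none uses month 12. The month-12 score enters only the descriptive change from baseline in Section 4.4.3.

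**Step 5: what would blinding at month 12 protect?** It would protect the month-12 ratings themselves, and it would keep the rating method the same as at months 3 and 6. The baseline is a separate matter. Sections 6.2 and 6.4 allow it to come from medical records up to 12 months before implant, with no blinding stated. A blinded rater at month 12 leaves that side of the comparison as it was.

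**Step 6: month-36 device testing.** Pointing away from blinding: plain X in Table 1, and month 36 missing from the lists in Section 4.2 and in the Blinded Evaluation paragraph. Pointing towards it: the synopsis, which treats months 3, 12 and 36 together; the Evaluation of Programming text, which requires a designated blinded evaluator during device testing and exempts no visit; and the 36-Month Visit paragraph, which repeats the earlier instructions. This is a conflict in the text, and the documents do not settle it.

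**The case against.** The strongest reply is that this is a deliberate and consistent choice. Blinded UPDRS III is confined to the two visits that feed a hypothesis test, and blinded evaluation is attached to the primary and secondary endpoints but not to the descriptive ones. That is correct for UPDRS III. The point is therefore an avoidable weakness and not a contradiction, and the descriptive status lowers its weight.

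Three further replies stand in part.

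- The listed endpoint is change from baseline, not the within-visit contrast between stimulation on and off. Blinding one end of an otherwise unblinded comparison gains only so much.
- The subjects' own blind to their settings ends after 6 months, and blinding the rater does not restore it.
- Section 6.6 recommends but does not require one person for both the window and UPDRS III, and the month-3 instructions, repeated at month 12, let device testing spread over several days of a week. The blinded evaluator is thus required at the visit but not necessarily present for the motor examinations, so the cost is small but not nil.

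A reader might also infer more than the documents support:

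- **That an apparent change after month 6 would be an artefact of rating method.** No month-6 to month-12 comparison of UPDRS III is planned, so this is not a main harm.
- **That the bias can be sized.** The documents give neither a standard deviation for UPDRS III change nor any figure for rater bias, so a calculated loss of coverage would only restate its assumptions.
- **That the month-36 window test is unblinded.** Half the relevant text says the opposite.

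**Conclusion.** The point holds for month 12. UPDRS III there may be rated by someone aware of the stimulation state, at a visit for which the plan already requires a blinded evaluator and in the same four states that are scored blind at month 3. The extent is four examinations at one visit and one descriptive endpoint; no hypothesis test is touched. The size of any bias cannot be stated from the documents.

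The conclusion rests on reading the absence of the asterisk, and of any named rater, as absence of a requirement. Three parts of the plan support that reading. A site could still choose to blind these ratings.

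Month 36 is secondary: an inconsistency over device testing, with UPDRS III at that visit depending on how it is resolved. This is an inexpensive improvement worth making, not a flaw that threatens the trial's main conclusions.

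**What to change.** **Month 12**

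- In Table 1, mark the four month-12 UPDRS III rows X*.
- In the 12-month visit list of Section 6.6, add to both UPDRS III lines the blinded-rater wording already used at month 3.
- Add month 12 to the statements of when UPDRS III is rated blind: the synopsis (Data Collection), Section 4.2 and the Blinded Evaluation paragraph of Section 6.6.

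**Month 36**

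- Reconcile Table 1, Section 4.2 and the Blinded Evaluation paragraph with the synopsis, the Evaluation of Programming text and the 36-Month Visit paragraph.
- If the blinded reading governs, have the same evaluator score UPDRS III at month 36, and amend the visit list, Table 1 and the general statements to match.

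**Cost.** A protocol wording change and a longer session for the evaluator already required at month 12, with some scheduling where the window test and the motor examinations fall to different people or days. The study report should still say that the baseline has no stated blinding and that the change from baseline is not a blinded comparison.

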### 24-Month Follow-Up Visit (24 months ± 90 days since initial programming)

The following information will be collected at the 24-month follow-up visit:

- AE and/or protocol deviation (if applicable). Adverse events will be reported on subjects who consent for participation in the long-term follow-up. The start date for reporting events will be the day of the previous PROGRESS follow-up visit, to ensure that all adverse events are reported. Adverse events will continue to be reported for the duration of the subject's participation in the long-term follow-up.

The 24-month visit may be performed in person or by telephone, at investigator decision. If consent for the long-term follow-up occurs after window for the 24-month follow-up visit has passed, it will be considered a missed visit with no protocol deviation required. The subject will be scheduled for the 36-month visit based on initial programming date.

### 36-Month Follow-Up Visit (36 months ± 90 days since initial programming)

The following information will be collected at the 36-month follow-up visit:

- PDQ-39;
- UPDRS part II ADLs On Medication / On Stimulation;
- UPDRS part III motor examination Off Medication/Off and On Stimulation;
- UPDRS part III motor examination On Medication/ Off and On Stimulation.
- Omnidirectional and directional testing - Off Medication;
- Programming parameters; device session data;

## Clinical Investigational Plan

- Unscheduled visits (if applicable);
- Current Parkinson's Disease medication;
- AE, system revision, and/or protocol deviation (if applicable).

### Evaluation of Programming/Device Testing:

Device testing is to be completed with the subject in the Off Medication state.

Subjects are to be instructed not to take their medication the night prior to or the morning of the study visit; or depending on the type of levodopa medication the subject is taking (i.e.; extended release or long acting) the investigator can use clinical judgement to determine an adequate length of time that the subject should be off medication prior to the testing.

**In order to minimize programming bias, each site will have a designated programmer and a designated blinded evaluator during the omnidirectional and directional device testing. The blinded evaluator will be unaware of the specific program changes made to the device parameters during each testing.**

### Initial Programming Visit

Each site will perform their standard monopolar review of each lead to determine the best contact selection for the subject followed by:

**Omnidirectional Testing** – Assessment of the contact that has been selected as providing the best clinical benefit. Omnidirectional testing is defined as:

- Any of the contacts on a 4 channel lead (1-4); or
- All 3 segments (A, B, and C) are activated on contact 2 or 3 of the 8 channel lead; or
- Contact 1 or 4 active on the 8 channel lead

Each lead will be assessed by a blinded evaluator for first meaningful therapeutic effect followed by assessment of first sustainable side effects.

As the amplitude is increased by the programmer, the therapeutic effect on the motor symptoms will be based on the blinded evaluator's clinical judgement.

First meaningful therapeutic effect will be determined by the blinded evaluator's clinical judgement of the benefit seen for the subject's primary motor symptoms (i.e.; first benefit seen in at least one of the cardinal symptoms of PD (Tremor, Rigidity, or Bradykinesia or other).

Once first therapeutic effect is determined, the site will test for side effects. The amplitude will continue to be increased slowly by the programmer until the first sustainable side effect is observed by the blinded evaluator.

Side effects will be documented based on the determination of the blinded evaluator.

The width of the therapeutic window is defined as the electrical current at which a sustained side effect appeared minus the electrical current at which a meaningful therapeutic benefit was obtained.

Subjects are to be programmed and remain programmed in an omnidirectional configuration from the initial programming visit until the 3-month visit. If in the investigator's opinion, omnidirectional

## Clinical Investigational Plan

configuration does not provide adequate therapy for the subject, the investigator may change the programming to allow the use of a directional configuration.

### **3-Month Visit - Device testing is to be completed with the subject in the Off Medication state.**

In order minimize bias and maintain the blind as much as possible for the blinded evaluator, the site's designated programmer will be asked to flip a coin to determine which testing configuration will be completed first ( "heads" will be designated as omnidirectional and "tails" will be designated directional). This is so that the testing is not always completed in the same order.

Omnidirectional testing will be repeated according to the instructions above.

A detailed directional lead/contact testing will also occur as tolerated by the subject. The testing will be completed in 2 steps for a total of 6 assessments. Each programming/detailed device testing can be performed over multiple days (within the same calendar week). Each lead will be assessed for first meaningful therapeutic effect followed by assessment of first sustainable side effects by the blinded evaluator.

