#### **Directional Testing:**

Step 1: 8 Channel Lead – Directional assessment of each individual segment of the contact (2 or 3) that has been selected as providing the best clinical benefit. Testing will be completed in the following configurations:

- Segment 2 or 3A; followed by;
- Segment 2 or 3B; followed by;
- Segment 2 or 3C.

Step 2 (optional): 8-Channel Lead - Directional testing of 2 segments on the same contact. Two segments may be activated together: Each of the following configurations may be tested for a total of 3 separate tests. Select contact 2 or contact 3 for testing based on the best clinical benefit from testing in Step 1:

- A and B activated; followed by;
- B and C activated; followed by;
- A and C activated.

For each of the above steps, the amplitude will be increased slowly by the programmer until the blinded evaluator confirms first therapeutic effect. As the amplitude is increased, the first therapeutic effect on the motor symptoms will be based on the blinded evaluator's clinical judgement..

First meaningful therapeutic effect will be determined by the blinded evaluator's clinical judgement of the benefit seen for the subjects primary motor symptoms (i.e.; first benefit seen in at least one of the cardinal symptoms of PD (Tremor, Rigidity, or Bradykinesia or other)). Once first therapeutic effect is determined, the site will test for side effects. The amplitude will continue to be increased slowly by the programmer until the first sustainable side effect is observed by the blinded evaluator. Side effects will be documented based on the determination of the blinded evaluator.

Clinicians should use clinical judgement to determine the amount of time required to rest between each lead segment evaluation. It is suggested to allow a minimum of at least a 2-minute rest period between each contact/segment testing. During the testing session the clinician will also rate the subject's fatigue level.

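### At month 3 the coin flip puts the omnidirectional test only first or last within a lead, so with Step 1 completed tests 2 and 3 are always directional and can be recognised by counting

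*Combined protocol and SAP*

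**What the plan says.** Section 6.6 (3-Month Visit) gives the coin flip as a way to limit bias and protect the evaluator's blind as far as possible. The programmer is to "flip a coin to determine which testing configuration will be completed first", with heads meaning omnidirectional and tails directional.

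- **Omnidirectional test.** Section 6.6 (Initial Programming Visit) defines it as "Assessment of the contact that has been selected as providing the best clinical benefit", that is, one test per lead. It is repeated at month 3.
- **Step 1.** Section 6.6 (Directional Testing) asks for "Directional assessment of each individual segment of the contact (2 or 3) that has been selected as providing the best clinical benefit". The list is in fixed order, beginning "Segment 2 or 3A; followed by" B and then C.
- **Step 2.** The same section describes "Step 2 (optional): 8-Channel Lead - Directional testing of 2 segments on the same contact", with up to three tests, also in fixed order.
- **Amount of testing.** The 3-Month Visit text says "A detailed directional lead/contact testing will also occur as tolerated by the subject", and then "The testing will be completed in 2 steps for a total of 6 assessments".

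Sections 4.2 and 6.6 (Blinded Evaluation; Evaluation of Programming/Device Testing) keep programming, device settings and program changes from the evaluator. No section conceals the order or the number of tests.

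Both currents that define the window, first meaningful benefit and first sustained side effect, are the evaluator's clinical judgement. Under 4.4.1 the widest directional window is compared with the omnidirectional one, and one successful lead makes the subject a success.

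**The concern.** The coin randomises the order of two blocks, and the omnidirectional block is a single test per lead. That test can therefore never fall between directional tests, and the middle of the sequence is always directional.

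An evaluator who recognises a directional test could, without intending to, call benefit a little earlier or a side effect a little later. The identifiable tests are all directional, so such leniency would widen directional windows only. Because the widest directional window decides the lead, one favoured test can be enough. The study compares a single proportion with a fixed 60% goal, so there is no control group in which the same leniency would cancel out.

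**Working it through.** **1. The plan's own count.** Three single-segment tests (Step 1) plus three two-segment tests (Step 2) make 6, the stated total. This supports reading Step 1 as three tests on one contact.

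**2. Orders within one lead** (O = omnidirectional).
- Step 1 only: O A B C or A B C O. The probability that a test is directional is 0.5, 1, 1, 0.5 by position. Tests 2 and 3 are certain: 2 of 3 directional tests.
- Full Step 2, known in advance: O is first or seventh, so tests 2 to 6 are certain: 5 of 6.
- Step 2 of unannounced length: only tests 2 and 3 are certain: 2 of 6.
- Step 1 cut short: 1 of 2 with two segments tested, 0 of 1 with one.
- If "Select contact 2 or contact 3 for testing based on the best clinical benefit from testing in Step 1" is taken to mean that Step 1 covers both contacts, there are six Step 1 tests and 5 of 6 are certain.

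**3. Two leads.** The text does not say whether the leads share a flip. Tested lead by lead, tests 2, 3, 6 and 7 of 8 are certain, or 4 of 6 Step 1 tests, with one flip or two. If one flip serves both leads, each mode is run across both leads and the evaluator sees the side, then the point at which the side changes reveals the coin and 5 or 6 of 6 are certain.

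**4. Mixed order.** With O in a random one of four positions, no test is certain; each is directional with probability 3/4.

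**5. Illustration. The reading SD, leniency, lead correlation and starting rates below are assumed, not taken from the documents.** Passing needs a one-sided 95% Clopper-Pearson bound above 0.60 (12.1.1). With the planned 66 subjects, 46/66 gives 0.591 and 47/66 gives 0.607, so 47 successes are needed. The model has a window SD of 0.5 mA, readings rounded to 0.1 mA, ties counted as failures, Step 1 only, and independent leads, so the per-subject rate is 1 − (1 − per-lead rate)².
- *No true difference, 0.25 mA leniency on tests 2 and 3:* per lead 72% to 81%, per subject 92% to 96%. The pass probability exceeds 99.99% already at 92%, so the decision does not change. The high start comes from taking the best of three, a separate matter.
- *Per-subject rate 59% without leniency* (segment windows averaging 0.59 mA narrower than omnidirectional): the pass probability is 3%. With 0.25 mA leniency it becomes 64% (rate 72%) if leniency applies in full to the certain tests only, or 20% (rate 66%) if it is proportional to the evaluator's belief that the test is directional.
- *Varying the 64% one assumption at a time:* leniency 0.1 or 0.5 mA gives 15% or over 99%; SD 0.3 or 1.0 mA gives 98% or 20%; success correlation between leads of about 0.25 or 0.5 gives 38% or 19%.
- *Proportional leniency and those correlations together:* about 13% or 8% at 0.25 mA, and about 5% or 4% at 0.1 mA.

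**6. Early stopping.** Probability that both modes have been tested after two and after three tests:

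| Order | After 2 | After 3 |
|---|---|---|
| Coin | 50% | 50% |
| O mixed among four tests | 2/4 = 50% | 3/4 = 75% |
| O drawn from all seven tests | 2/7 = 29% | 3/7 = 43% |

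**7. Step 2 after a mixed Step 1.** Tests 5 to 7 are then certain: 3 of 6, against 2 of 6 (unannounced) or 5 of 6 (known in advance) with the coin. In the same model with no true difference and 0.25 mA leniency, per-lead success with Step 2 counted is 89%, against 88% or 91% with the coin and 84% without leniency.

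**The case against.** The mechanism is conditional. The evaluator must know the scheme, count tests within a lead, and lean towards directional stimulation; none of this is documented. The plan claims the blind only as far as possible, and the duty to keep settings from the evaluator is stated in several places. That all stands, but hiding settings does not prevent inference by counting, and a mixed order conceals more with the same tests.

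The borderline illustration is also open to attack. It places the true rate just below the goal, which in this model needs directional windows clearly narrower than omnidirectional ones, whereas the acute study cited in section 2.0 reported a directional window 41.3% wider. At the planned 75% success rate (12.2) the alternative is true anyway. This stands too, and is why the figures are only a range under assumptions.

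A reader might infer that evaluators were in fact unblinded, or that a pass would owe something to leniency. The documents support neither. With Step 1 only, counting within a lead does not even reveal the omnidirectional test, which remains a 50/50 guess between first and last.

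Finally, mixing helps little where Step 2 is used, and drawing the omnidirectional position from all seven tests would more often leave a lead without both windows. Directional testing is done only as tolerated, the analysis needs both windows, and nothing is imputed (12.1.1, 12.9). That objection is accepted and limits the fix to Step 1.

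**Conclusion.** The concern holds as a design weakness. Within an 8-channel lead with Step 1 completed, an evaluator who knows the scheme and counts could identify 2 of 3 Step 1 directional tests, and a concealed mixed order would make none certain. The count rests on reading Step 1 as three tests on the one selected contact.

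The effect on pass or fail cannot be quantified from the documents. Under the stated assumptions, with a 59% per-subject rate and 0.25 mA leniency, the chance of passing rises from 3% to between about 20% and 64% according to how leniency follows belief. It is lower if leads are correlated or leniency is smaller, and higher if leniency is larger or readings less variable. With no true difference in that model the decision does not change. The change is worth making because it is cheap and serves the coin's stated purpose, not because bias has been shown.

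**What to change.** - In 6.6, for remaining 3-month and 12-month tests, replace the coin by a pre-generated random order for each lead that mixes the omnidirectional test with the three Step 1 segment tests. The programmer holds it, does not show it to the evaluator, records it on the CRF, and finishes one lead before starting the other.
- Keep optional Step 2 after this set. Do not draw the omnidirectional position from all seven tests.
- Because Step 2 tests remain identifiable, add a sensitivity analysis of the primary endpoint using only Step 1 and omnidirectional windows. Report how often the widest window came from Step 2 and which order procedure each subject had.
- Reconcile the stated total of six assessments with the optional status of Step 2.

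**Cost.** Tests, staff and visits are unchanged, and the sensitivity analysis uses windows already collected. The change needs an order list per site (up to 60 centres), a protocol amendment notified to or approved by ethics committees where required (14.0), and mode switching within a session. If most month-3 tests are already done, the 66-subject set gains little and mixes two procedures; the sensitivity analysis and reporting of the widest window's source remain useful.
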